The Stanford Parkinson's Disease Plasma Study (SPDP)

NCT02968433

CLINICAL PROTOCOL

07/23/2018

**[name], Principal Investigator
Stanford University**

[name]

1. Protocol Title

The Stanford Parkinson's Disease Plasma (SPDP) Study: Intravenously-Administered Plasma From Young Donors for Treatment of Moderate Parkinson's Disease

Principal Investigator / Protocol Director: [name] MD MSE
Sponsor: Donation (anonymous)

2. Purpose of the Study

The purpose of this study is to demonstrate that plasma infusions can be performed safely in patients with Parkinson's Disease (PD). Secondary outcomes will include behavioral and laboratory data that will support the next study that will inquire whether young plasma infusions improve or slow the progression of cognitive, mood and/or motor impairment and rate markers of the disease.

3. Background & Significance

Parkinson's disease (PD) is a neurodegenerative disease that affects over 1.6 million people in the United States and whose incidence increases with age, affecting over 1% of people over the age of 65. The neuropathological processes involved in PD are widespread throughout the brain, and are reflected in a constellation of motor, cognitive, mood and other non-motor symptoms. Treatments to date have largely focused on dopamine replacement strategies or deep brain stimulation, both symptomatic treatments.

As neurodegenerative diseases progress, there are major changes throughout the body and brain. These changes are transmitted in the body via the circulatory system between organs, tissues and cells. Recent findings from multiple laboratories have shown that infusions of young plasma into aging rodents can have beneficial effects on cognitive functions, as well as on some biomarkers of aging. This suggests that the circulating components of plasma can improve cognitive and disease-relevant symptoms (Villeda et al, 2011; Villeda et al, 2014). This has motivated the field to treat multiple disorders with blood products and their constituent active components.

The established safety of blood transfusions allows us to test whether infusion of young plasma can ease the neurological symptoms in human subjects with neurodegenerative diseases. A study that is ongoing at Stanford, in the department of Neurology and Neurological Sciences, is testing whether infusions of young plasma can ameliorate the cognitive impairment in patients with Alzheimer's disease (ClinicalTrials.gov identifier NCT02256306). To date, this has been well-tolerated by the subjects, without major adverse effects.

We propose to test the safety and efficacy of transfusing young plasma into PD patients, in order to establish its effects on motor and cognitive functions in patients in a Phase 1 study. The successful completion of this study will inform the design of future,

larger and multicenter studies with the goal to determine whether infusions of young plasma can ameliorate the neurodegenerative symptoms and underlying pathophysiology in Parkinson's disease.

4. Selection of Subjects

- The goal number of subjects completing the study is 15
- Subjects will sign an informed consent approved by the Stanford IRB

Inclusion criteria

- Subjects are to be between the ages of 50 – 80.
- A diagnosis of clinically probable or established Parkinson's Disease (MDS criteria)
- Subject must be on a stable dose of dopaminergic medication and/or DBS parameters for at least 4 weeks prior to screening and for the duration of the study
- Must have Montreal Cognitive Assessment (MOCA) score between 23-28, and have cognitive complaints
- Subject must be competent to sign consent
- Subject must be willing to commit to being available for twice weekly infusions and testing for 4 consecutive weeks and for testing one month later.
- The availability of a study partner who knows the patient well and is willing to accompany the subject to all trial visits, to participate in questionnaires and to complete daily journal assessments. Note: optional partner participation if participant is able to consent and travel by self.

Exclusion Criteria

- The participation in any other interventional therapeutic clinical trial during the study
- The inability to travel to Stanford
- Inability to walk without assistance in the off or on medication state
 - Must not exceed a Hoehn and Yahr score of 4
- The clinically determined presence of dementia
- A clinical suspicion/diagnosis of MSA, PSP LBD, ET
- Subject's pregnancy or likelihood of pregnancy within the next 6 months.
- Subject's positive test results for Hepatitis B, Hepatitis C or HIV at screening
- Any other condition or situation that the investigator believes may interfere with the safety of the subject or the intent and conduct of the study
- Subject's medical history of:
 - Stroke

- Anaphylaxis
- Gout- may cause an increase in uric acid
- Prior adverse reaction to any human blood product
- Any history of a blood coagulation disorder or hypercoagulability
- Congestive heart failure
- Uncontrolled hypertension
- Renal failure
- Prior intolerance to intravenous fluids
- Recent history of uncontrolled atrial fibrillation
- IgA deficiency (by history)
- Subject's relation to medications or other treatments:
 - Any concurrent use of an anticoagulant therapy. Antiplatelet drugs (e.g., aspirin or clopidogrel) are acceptable.
 - The use of Inosine, which may alter urate levels
 - Concurrent participation in another interventional treatment trial for Parkinson's disease. If there was prior participation, the last dose of the investigational agent must have been at least 6 months prior to Screening.
 - Treatment with any human blood product, including intravenous immunoglobulin, during the 6 months prior to Screening or during the trial.
 - Concurrent daily treatment with benzodiazepines, typical or atypical antipsychotics, long-acting opioids, or other medications that, in the investigator's opinion, interfere with cognition. Intermittent treatment with short-acting benzodiazepines or atypical antipsychotics may be permitted, provided that no dose is administered within the 72 hours preceding any cognitive assessment.

Ineligible Subjects

Ineligible subjects will be notified of their ineligibility. Ineligible subjects will be asked if their information could be kept on files in the event of being qualified to participate in future studies. If subjects do not want their information on file, all data collected will be destroyed. Only participating subjects will be used for analysis.

5. Design & Procedures

We will evaluate a dose of one Plasma unit transfusion twice per week (obtained from male subjects between the ages of 18-25) for four weeks in 15 study subjects with PD. The study will be open-label and an end point at eight weeks after the first week of transfusions.

The plasma will come from Stanford's Blood Center (SBC), not an external company. The Plasma product will be stored in the SBC, later transported to Stanford Transfusion Services before infusions. Infusions will take place in a Stanford Infusion Center. The primary objective of the study is to assess the safety and tolerability of twice weekly plasma transfusions. The secondary objectives are to assess the effect of twice weekly plasma transfusions in subjects with PD on motor function: United Parkinson's Disease Rating Scale (UPDRS), objective kinematic measures, cognitive function (detailed neuropsychological battery), and the Montreal

Cognitive Assessment (MoCA) as well as assessing plasma biomarkers through blood laboratory work.

- Donors must be:
 - Male- To minimize transfusion risks, only young male plasma will be used since female plasma has been linked to the possibility of Transfusion-Related Acute Lung Injury (TRALI), linked to immune cells carried by women who have been pregnant
 - Between the ages of 18-25
- Targeted availability of plasma within 2 weeks of completion of ABO/Rh typing.

Protocol

- **Initial screening** to evaluate the subject's candidacy based on the inclusion/exclusion criteria
- Health history and review of systems will be conducted
- Medication review
- Physical and neurological examinations: the Montreal Cognitive Assessment (MoCA), Unified Parkinson's Disease Rating Scale (UPDRS III and IV), and quantitative kinematics (physical): rapid Wrist Flex Extension (rWFE), Quantitative DigitoGraphy (QDG), Stepping in Place (SIP), and analysis of gait (GaitRite) ON and OFF medication (2 day visit), Freezing of Gait Questionnaire (FOG-Q), Stepping In Place questionnaire (SIP-Q)
 - *Subject will be asked to bring their own dosage of short acting Parkinson's Disease medicine to take after kinematic testing (Carbidopa / Levodopa) for OFF MEDS visit.
 - **When subject has signed consent and has been enrolled, notify the blood bank and transfusion service to order the plasma units.
- EKG
- **Baseline Assessment** (may occur immediately follow Screening, or occur on another day *within 2 weeks* of the first plasma transfusion) of the following will be conducted
 - Neurocognitive assessments: Trail Making Test A& B, Digit Symbol Test, Animal Naming Test, Phonemic Fluency (FAS), Matrix Reasoning, Block Design, Cogstate Maze Learning Test (Cog State)
 - Neuropsychiatric assessments: Beck Anxiety Inventory (BAI), Beck Depression Inventory (BDI), Parkinson's Disease Quality of Life Scale (PDQ-39)
 - Blood draw: 12 mL blood for central banking (these samples will be de-identified prior to further analysis and will be coded with a sample number, time of day and date of blood draw.
 - Blood Labs: metabolic and hematologic panels, Prothrombin Time (PT), Partial Prothrombin Time (PTT), Human Immunodeficiency Virus screen, Hepatitis B screen, Hepatitis C screen, IL6, uric acid, Apolipoprotein-

A1, direct bilirubin, homocysteine, ferritin, TNF, HIV Ag/Ab screen, ABO/Rh Typing and verification prior to first test agent administration

- **Plasma Transfusions (*starting within 2 weeks* of Baseline Assessment)**
 - Administer test agent twice weekly for 4 weeks (see transfusion protocol below)
 - Concomitant medication review
 - Adverse event/tolerability review, Flow Sheet-recording of vitals
 - Adverse events review per transfusion center protocol

- **Interim Assessment (on the week of last transfusion)**
 - Motor/Physical (ON and OFF medication)- UPDRS III/ IV, SIP, rWFE, QDG, GaitRite/FW, SIP-Q, FOG-Q
Neurocognitive assessments: Trail Making Test A& B, Digit Symbol Test, Animal Naming Test, Phonemic Fluency (FAS), Matrix Reasoning, Block Design, CogState Maze Learning Test (Cog State), ON medication
 - Neuropsychiatric assessments: Beck Anxiety Inventory (BAI), Beck Depression Inventory (BDI), PDQ-39, ON medication
 - Blood Draw (Lab collect)
 - Blood draw: Metabolic and Hematologic Panels, inflammation set

- **Final Assessment (*4 weeks after last transfusion*)**
 - Motor/Physical (ON and OFF medication)- UPDRS III/ IV, SIP, rWFE, QDG, GaitRite/FW, SIP-Q, FOG-Q
 - Neuropsychiatric assessments (BDI, BAI, PDQ-39), ON medication
 - Neurocognitive assessments Trail Making Test A& B, Digit Symbol Test, Animal Naming Test, Phonemic Fluency (FAS), Matrix Reasoning, Block Design, CogState Maze Learning Test (Cog State), ON medication
 - Blood Labs: Metabolic and Hematologic Panels, inflammation set,
 - Blood Draw: 12 mL blood for central banking

- **Transfusion Protocol**
 - Perform the transfusion according to the most current “Blood and Blood Component Administration” guidelines at Stanford Hospital & Clinic; in brief:
 - Check and record pre-transfusion baseline vital signs (temperature and blood pressure) within 1 hour prior to transfusion.
 - Obtain IV access
 - Infuse test agent at 1-2 ml/min for the first 15 minutes while observing the subject closely for any adverse reaction.

- Record the vital signs at 15 min.
- If vital signs are normal or unchanged, then increase infusion rate to as fast as tolerated, or approximately 250-300 ml/hour.
- Continue to monitor the subject for signs/symptoms of adverse reaction during the entire infusion.
- For any suspected transfusion reaction, report immediately to the Principal Investigator, [name], or designated on-call study physician, [name], and follow the detailed “Blood and Blood Component Administration” guidelines.
- Record vital signs 15 min after completion of the infusion
- The subject should remain at the infusion facility under nursing supervision throughout the entire transfusion procedure until 30 minutes after completion of the infusion. If post-transfusion vital signs are normal and there is no sign or symptom of an adverse reaction, then the subject is free to go. Instructions will be provided to the subject and study partner about whom to contact and what to do in an emergency, if a delayed transfusion reaction is suspected.
- Retain a ~1 ml sample of the test agent in the unit after infusion.

6. Subject Recruitment and Compensation

Subjects will be recruited through Stanford’s Clinic, The Michael J. Fox Foundation trial finder, listings in Clinicaltrial.gov, from previous experiments, and by personal interest in the study. Subjects recruited from previous experiments will have consented to be contacted for future experiments. Potential subjects will need to meet all inclusion criteria and none of the exclusion criteria. A reimbursement budget of \$200 per subject will cover parking and travel related expenses.

7. Consent Process

Prior to introducing a consent form, the subject will receive a thorough description of the purpose of the study, the design of the study, potential risks and discomforts throughout and after the study, as well as the benefits (if any direct benefits) of participating of this study. After being informed, the subject will be presented with the consent form delineating previously stated information about the participation of this study. The subject undergoing the trial will be responsible for giving consent.

8. Subject’s Capacity to Give Legally Effective Consent:

Upon the inability to provide consent, diminished capacity will be assessed by a series of cognitive assessments to provide a clear position on whether subject has enough cognitive capacity to participate in this study. Cognitive assessments will be administered prior to starting the study.

9. Study Interventions:

Implanted devices included but not limited to birth control methods, heart pacers, brain stimulators, etc. may intervene with the study. Subject will be asked if they have any implanted devices during prescreening.

10. Risk/Benefit Assessment:

Blood products carry risks of virus, hepatitis and HIV infection. Acute transfusion reactions could include such signs and symptoms as the following, divided into classes to denote the level of severity.

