***Class 1:**

- Urticaria (a type of rash)

- Hives

Class 2:

- Fever

- Chills

- Nausea

Class 3:

- Low Hematocrit (which refers to the percentage of whole blood that is made up of red blood cells) without evidence of bleeding

- High bilirubin fever (meaning there is a higher level of waste that hasn't been filtered out as it usually is when red blood cells breakdown).

Class 4:

- Oliguria (a reduction in the amount of urine being passed)

- Bleeding

- Hemoglobinemia (an excess of hemoglobin in the blood plasma)

- Hemoglobinuria (hemoglobin—the oxygen-transporting protein in blood—is at abnormally high levels)

- Transfusion associated circulatory overload

- shock

NOTE: * Class 1 reactions are to be expected and considered within normal range for this study

The subject will be observed during each transfusion for signs and symptoms of acute hemolytic reaction (i.e., chills, fever, low back pain, flushing, tachycardia, tachypnea, hypotension, red urine, shock, cardiac arrest). The subject will also be monitored

during the transfusion to minimize risk for potential infiltration or fluid overload due to rapid infusion of red blood cells (RBCs) or blood components.

Subjects with severe anemia and congestive heart failure are sensitive to circulatory overload.

The subject may also experience delayed transfusion reactions several hours to several days (delayed hemolytic reaction) after the transfusion is completed. Such reactions can include a febrile or pulmonary reaction (up to 6 hours) that may be associated with the blood administration.

Risks may include but not limited to transfusion reactions, bruising and/or soreness of arm in involved area, fatigue, boredom, and restlessness. To reduce the potential of any risks, subjects will be routinely asked for feedback on their current state. Some risks, such as arm bruising and soreness will be minimized by administration of procedure conducted only by qualified individuals. In the event of special precautions to be taken, such as the case of use of vulnerable populations (cognitively impaired adults), cognitive assessments before each session will be conducted to ensure the subjects ability to communicate any discomforts throughout the study.

- All adverse reactions reported after the start of the transfusions will be documented during trial.

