- Transfusion reaction is an adverse event of a special interest, and any subject who experiences a transfusion reaction, in the opinion of the Transfusion Service or [name] and [name], will not be allowed to receive any further infusion.
 - In the event of discontinuation of infusions due to a transfusion reaction or other serious adverse event, a safety and efficacy follow-up assessments will take place 1 week after the last transfusion.

11. Cost to the Subject:

There will be no cost for the subjects; the subject will not be expected to pay for research participation.

12. Data Analysis & Statistical Considerations:

Endpoints include

- Primary Outcome Measure:

- Number of subjects with adverse events as a measure of safety and tolerability, and number of subjects who comply with the research protocol as a measure of feasibility.
- Secondary Outcome Measures:
 - Change on the UPDRS III/ IV off medication
 - Change in gait speed
 - Change in quantitative kinematics, FOG-Q
 - Change on the Parkinson's Disease Quality of Life Scale (PDQ-39)
 - Change on the Beck Anxiety Inventory (BAI)
 - Change on the Beck Depression Inventory (BDI)
 - Change in Trail Making Test A& B, Digit Symbol Test, Animal Naming Test, Phonemic Fluency (FAS), Matrix Reasoning, Block Design and Cogstate Maze Learning Test (Cog State)
 - Change in plasma biomarkers

13. Data & Safety Monitoring

Safety concerns regarding subject data include loss of subject data and disclosure of identification of participants. All electronically connected data will be securely stored in Stanford Medicine Box with Protected Health Information (PHI) & Personally Identifiable Information (PII) protection. Persons with access to this information include the Primary Investigator, research coordinator, and research team collecting data. Frequency of data monitoring will be as needed for data processing.

To ensure the subject's data and physical safety, continuous safety monitoring will occur throughout the study by the Safety Review Committee. The Safety Review Committee will include an on-call Neurologists, [name], [name], Psychologist [name], [name] and [name].

For any AEs outside of Stanford facility, the subject must call the research assistant at [name]. The research assistant will report AE to primary investigator and [name]. The subject will be told to seek medical assistance in nearest Emergency Department by them.

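### Scheduled adverse-event review is not required to precede the next plasma unit and stops at Visit 11, so late reactions after the eighth unit reach the primary count mainly through calls the subject initiates

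*Combined protocol and SAP*

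**What the plan says.** Section 12 makes the number of subjects with adverse events the primary safety measure. Section 10 describes late reactions: "The subject may also experience delayed transfusion reactions several hours to several days" after a transfusion. It also says that a subject judged to have had a transfusion reaction receives no further infusion.

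Adverse events can be captured in three ways.

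- **Scheduled review.** Table 1 marks the adverse-event and tolerability row at Visits 4 to 11, the eight transfusion visits. The row is blank at Visits 12 to 15. The Interim and Final Assessment lists in Section 5 contain no adverse-event review either.
- **Subject-initiated calls.** Section 13 states: "For any AEs outside of Stanford facility, the subject must call the research assistant". The assistant informs the investigator, files a report and documents the event. The Transfusion Protocol in Section 5 adds: "Instructions will be provided to the subject and study partner about whom to contact" if a delayed reaction is suspected.
- **A daily journal.** Section 4 lists it among the study partner's tasks and then relaxes the requirement. The partner is to be willing "to participate in questionnaires and to complete daily journal assessments. Note: optional partner participation if participant is able to consent and travel by self". The journal is not mentioned again in Section 5, Section 12 or Table 1.

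**The concern.** Two things depend on finding a delayed reaction in time. The first is the rule in Section 10 against further infusion, which can be applied before the next unit only if someone has asked what happened since the last one. The second is the primary count, which is complete only if every post-infusion period ends with the same question put to every subject. The plan secures neither. The review at a transfusion visit may take place after that day's unit has started, and the period after the last unit has no review. The item that could have helped, a daily record, is left undefined and has no keeper when the partner is waived.

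**Working it through.** The plan gives no figure to reproduce. The check sets the timing of delayed reactions against the schedule.

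**Inputs.** Eight transfusions per subject, two a week for four weeks (Section 5, Table 1). Goal of 15 completers (Section 4). Visit 12 is the day after the last transfusion and Visit 14 is four weeks after Visit 12 (Table 1); Section 5 puts the Final Assessment four weeks after the last transfusion.

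**Step 1: periods that end in a scheduled review.** Each of the eight transfusions opens a period in which a delayed reaction could appear.
- Periods 1 to 7 end at Visits 5 to 11, each marked for review: 7 per subject, 7 × 15 = 105 in all.
- Period 8 runs from Visit 11 to the final assessments, with no review marked: 1 per subject, 1 × 15 = 15 in all.
- Total 8 × 15 = 120, so 15/120 = 12.5% of the periods end without a scheduled review.

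**Step 2: length of the uncovered period.** By Table 1 the time from the eighth unit to Visit 14 is 1 + 28 = 29 days; by Section 5 it is 28 days. Either is far longer than the several days over which Section 10 expects delayed reactions.

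**Step 3: order within Visits 5 to 11.** Twice weekly means one unit every 7/2 = 3.5 days on average; exact spacing is not stated. A reaction that takes several days to appear can therefore surface close to the next visit. Before the infusion starts, the Transfusion Protocol lists vital signs and venous access. It contains no question about events since the previous unit. The Section 5 list for transfusion visits names adverse-event review after administration. List order does not prove order in time, but no sentence requires the review to come first.

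**Step 4: effect on the primary count.** The outcome counts each subject once. Missing a late event matters only if the subject has no other counted event, and the error can only lower the count. One such subject among 15 changes the proportion by 1/15 = 6.7 percentage points.

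**Step 5: whether the journal closes the gap.** It has no stated content, no row in Table 1 and no use in Section 12. The waiver has two conditions. The first, ability to consent, excludes nobody, because eligibility already demands it: "Subject must be competent to sign consent". The second, travelling alone, is narrower than the exclusion for "The inability to travel to Stanford", and the share of subjects who meet it is not given. When the partner is waived, nobody is named to keep the journal. As written, it cannot be relied on as a safety record for any subject.

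**The case against.** The strongest reply is that adverse events are well covered. Every subject, with or without a partner, must call in events that occur outside the facility, and these are documented. Section 10 says that all reported reactions after the start of transfusions are recorded and that subjects are routinely asked how they are. It also promises cognitive assessments before each session to protect subjects' ability to report discomfort. Blood panels at Visits 12 and 14 could show laboratory signs of a late reaction. After discontinuation for a reaction or other serious event, there is a safety follow-up at one week. The transfusion steps are explicitly a summary of hospital guidelines that are not reproduced, and those may include a check before the unit.

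Much of this stands. A reader might infer that the journal is the only record between visits; the call route in Section 13 shows that it is not. A reader might also infer that nearly every subject will lack a partner, or that the count will depend on who brought one. The documents give no share of subjects able to travel alone and never say that the journal records adverse events, so neither inference is supported.

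The reply does not supply a scheduled question after the eighth unit or a stated order before the next one. Calls depend on the subject recognising and reporting an event, in a group selected for cognitive complaints. Table 1 marks no cognitive test at Visits 4 to 11. Asking about current state is not a look-back over the days since the last visit, and blood panels do not capture symptoms. The one-week follow-up does not apply to subjects who complete treatment.

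**Conclusion.** The concern holds as a gap in scheduled capture. For subjects who complete treatment, the last of eight post-infusion periods, 28 or 29 days long, has no scheduled adverse-event review: 15 of 120 periods if 15 subjects complete. For the other 105, a review is marked, but the protocol does not say that it comes before the next unit. The effect on the primary outcome can only be an undercount, at 6.7 percentage points for each subject whose only event is missed. How many would be missed cannot be estimated, because the documents give no reaction rate and no detection rate. Uneven capture by partner status is a possibility if journals are informally used as a source; it is not established. The conclusion rests on Table 1 and the Section 5 visit lists agreeing that no review is planned at Visits 12 to 15, and on the hospital guidelines not being available to settle the order at Visits 5 to 11. In a study whose main purpose is safety, this should be corrected.

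**What to change.** - **Table 1 and the Section 5 Interim and Final Assessment lists:** add adverse-event and tolerability review at Visits 12 and 14.
- **Section 5, transfusion visits:** state that the look-back since the previous visit is done before the unit is started at Visits 5 to 11, so that the existing rule in Section 10 can be applied with the information in hand.
- **Section 4:** have the subject keep the daily journal when no partner takes part, and define what it records.
- **Table 1:** add a journal row from Visit 4 to Visit 14, with the journal read at each adverse-event review.
- **Section 12:** name the journal as an adverse-event source for all subjects, alongside visit reviews and calls, and record for each subject whether a partner took part.

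The cost is a short diary and a few minutes at visits already planned. More active questioning may raise the number of minor events reported. No visit is added, and no dose, infusion interval or stopping rule is changed.
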